10.4.1. Total vaccinated cohort

- The TVC analysis will be performed per treatment actually administered. A safety analysis based on the TVC will include all subjects with the study vaccine administration documented.
- An immunogenicity analysis based on the TVC will include all subjects vaccinated and for whom data concerning at least one immunogenicity endpoint measure is available.

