- For a given subject and the analysis of solicited symptoms during the 4-day post-vaccination follow-up period, missing or non-evaluable measurements will not be replaced. Therefore, the analysis of the solicited symptoms based on the TVC will include only vaccinated subjects and doses with documented safety data (i.e. symptom screen completed).
- For analysis of unsolicited AEs, such as SAEs or AEs by primary MedDRA term, and for the analysis of concomitant medications, all vaccinated subjects will be considered. Subjects who did not report the event or the concomitant medication will be considered as subjects without the event or the concomitant medication, respectively.
- For summaries reporting both solicited and unsolicited AEs, all vaccinated subjects will be considered. Subjects who did not report the event or the concomitant medication will be considered as subjects without the event or the concomitant medication, respectively.

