10.8. Analysis of safety

The analysis will be based on the TVC.

- The percentage of subjects reporting each individual solicited local and general symptom during the 4-day (Day 1-4) follow-up period after booster vaccination will be tabulated. The same calculations will be done for each individual solicited symptom rated as grade 3 in intensity and for each individual solicited symptom assessed as causally related to vaccination.
- Occurrence of fever during the 4-day follow-up period after vaccination will be reported per 0.5°C cumulative increments.
 - In addition, the above analysis will also be done for sub groups based on age stratification (Refer [Table 23](#)) as an exploratory analysis.
- The percentage of subjects with at least one local symptom (solicited or unsolicited), with at least one general symptom (solicited or unsolicited) and with any symptom (solicited or unsolicited) during the 4-day (Day 1-4) follow-up period after booster vaccination will be tabulated with exact 95% CI after booster vaccination. The same calculations will be done for symptoms (solicited or unsolicited) rated as grade 3 in intensity, for symptoms (solicited or unsolicited) leading to medical consultation and for symptoms (solicited or unsolicited) assessed as causally related to vaccination.
- The percentage of subjects who started to receive at least one concomitant medication (i.e. any medication, antipyretic medication, prophylactic antipyretics) during the 4-day (Day 1-4) and 31-day (Day 1-31) follow-up period after vaccination will be tabulated with exact 95% CI.

- The verbatim reports of unsolicited AEs will be reviewed by a clinical research and development lead and the signs and symptoms will be coded according to MedDRA. Every verbatim term will be matched with the appropriate Preferred Term. The percentage of subjects with unsolicited AEs occurring within the 31-day (Day 1-31) follow-up period after booster dose with its exact 95% CI will be tabulated by Preferred Term. Similar tabulation will be done for unsolicited AEs rated as grade 3 and for unsolicited AEs with causal relationship to vaccination.
- Any large injection site reaction (for subjects <6 years of age defined as a swelling with a diameter of >50 mm and for subjects ≥6 years of age swelling with a diameter of >100 mm, noticeable diffuse swelling or noticeable increase in limb circumference) onset during the 4-day (Day 1-4) follow-up period after vaccination will be described in detail.

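### Combined Day 1-4 reactogenicity summaries count vaccinated subjects without a symptom screen as symptom-free, so any such subjects can only pull those percentages down

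*Protocol*

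**What the plan says.** Protocol section 10.5 sets two missing-data rules for the same four days.

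- **Individual solicited symptoms.** Missing measurements are not replaced, and "the analysis of the solicited symptoms based on the TVC will include only vaccinated subjects and doses with documented safety data", which the section equates with a completed symptom screen.
- **Combined summaries.** "For summaries reporting both solicited and unsolicited AEs, all vaccinated subjects will be considered". The next sentence settles how silence is read: "Subjects who did not report the event or the concomitant medication will be considered as subjects without the event".

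Section 10.8 plans both kinds of table. One gives "The percentage of subjects reporting each individual solicited local and general symptom during the 4-day (Day 1-4) follow-up period". The other gives the percentage with at least one local symptom, with at least one general symptom, and "with any symptom (solicited or unsolicited) during the 4-day (Day 1-4) follow-up period after booster vaccination will be tabulated with exact 95% CI". The combined percentages are repeated for grade 3 symptoms, and "for symptoms (solicited or unsolicited) leading to medical consultation and for symptoms (solicited or unsolicited) assessed as causally related to vaccination".

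The only denominator that section 10.8 names is the cohort: "The analysis will be based on the TVC". Section 10.4.1 defines that cohort for safety: "A safety analysis based on the TVC will include all subjects with the study vaccine administration documented". The combined tables therefore fall under the second rule. Nothing in the protocol exempts subjects without a screen from it.

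**The concern.** Reading silence as absence is reasonable for unsolicited AEs and SAEs, which are captured because someone reports them. Solicited symptoms are different. The glossary describes them as actively solicited over a set period, so without a completed screen their absence has not been observed. The first rule in section 10.5 accepts this. The second sets it aside for composites that contain the same symptoms.

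A subject with no screen is thus missing from the individual table and symptom-free in the combined table. The resulting error in the combined percentage can only be downward, and the exact confidence interval treats the imputed subjects as observed. An any-symptom rate could even be printed below the rate of one symptom it contains.

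What is at stake is modest: the accuracy of descriptive summaries that support the reactogenicity and safety objective in section 2.2.

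**Working it through.** **The plan's own figure.** Section 10.3 asks for 100 evaluable subjects in each of four age groups with 10% drop-out. 100 / 0.90 = 111.1, rounded up to 112, and 4 × 112 = 448. This reproduces. The protocol states no symptom rate and no rate of missing screens.

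**Inputs.** N = 448 (section 10.3). The rest are assumptions:

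- r, the symptom rate among documented subjects: 70%.
- m, the fraction of vaccinated subjects with no screen and no other recorded Day 1-4 event of that kind: 1%, 2%, 5%, 10%.
- s, the unobserved symptom rate in that fraction: 30%, 70%, 100%.
- No events are recorded in subjects without a screen.

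**Formulas.**

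- True rate = r(1 − m) + s × m.
- Rate reported under the all-vaccinated rule = r(1 − m).
- Shortfall = s × m.
- Error of the completed-screen rate = r − [r(1 − m) + s × m] = (r − s) × m.

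**Results, in percentage points.**

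| m | Reported rate | Shortfall, s = 30% | Shortfall, s = 70% | Shortfall, s = 100% | Completed-screen error, s = 30% / 70% / 100% |
|---|---|---|---|---|---|
| 1% | 69.3% | 0.3 | 0.7 | 1.0 | +0.4 / 0 / −0.3 |
| 2% | 68.6% | 0.6 | 1.4 | 2.0 | +0.8 / 0 / −0.6 |
| 5% | 66.5% | 1.5 | 3.5 | 5.0 | +2.0 / 0 / −1.5 |
| 10% | 63.0% | 3.0 | 7.0 | 10.0 | +4.0 / 0 / −3.0 |

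**In whole subjects, with exact 95% confidence intervals.**

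| No screen | Completed-screen denominator | All vaccinated |
|---|---|---|
| 9 | 307/439 = 69.9% (65.4-74.2) | 307/448 = 68.5% (64.0-72.8) |
| 22 | 298/426 = 70.0% (65.4-74.3) | 298/448 = 66.5% (61.9-70.9) |
| 45 | 282/403 = 70.0% (65.2-74.4) | 282/448 = 62.9% (58.3-67.4) |

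With 9 subjects missing, the all-vaccinated interval has a half-width of (72.8 − 64.0) / 2 = 4.4 points, so the shortfall of about 1.4 points lies well inside it.

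**Low-rate versions.** If s = 5% and m = 5% are assumed, as might suit a grade 3 summary, s × m = 0.25 points.

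**Inversion.** A single symptom with documented rate p exceeds the reported composite when r(1 − m) < p, that is, when m > 1 − p/r. With r = 70%, this needs m above 1 − 68/70 = 2.9% for p = 68%, and above 1 − 65/70 = 7.1% for p = 65%.

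**Which denominator errs more.** For s below r, the completed-screen error (r − s) × m exceeds s × m when s < r/2, here below 35%. Above that point the all-vaccinated rule errs more.

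**The case against.** The strongest reply is that nothing here is contradictory. Section 10.5 states a rule for each type of summary. A combined table also holds unsolicited AEs, which properly belong on all vaccinated subjects, so a mixed table must follow one parent rule or the other, and the plan prespecified one. This stands as far as it goes: the point is the consequence of an explicit rule, not an inconsistency in the text. Because the protocol fixes the rule, it is also not a detail left to the SAP.

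The completed-screen denominator is not plainly better either. It errs more when s < r/2, and it drops events recorded in subjects without a screen. This stands, and it argues against simply swapping one denominator for the other.

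A reader might infer three stronger things that the documents do not support.

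- **That the combined rates are certainly understated, by several points.** The effect needs m > 0. Section 5.6.13 has unreturned cards sought by telephone or other means, the Table 6 footnote in section 5.5 adds retrieval of cards not sent in, section 9.2.1 keeps data up to last contact, and section 5.6.12 gives large injection site reactions their own eCRF screen. All of this keeps m small.
- **That the 10% drop-out in section 10.3 estimates m.** It allows for early withdrawal when sizing the evaluable cohort. It is not a rate of missing symptom screens, so the 10% row is only an upper illustration.
- **That a listed safety endpoint is biased.** Section 10.2 lists each solicited symptom, large swelling reactions, unsolicited AEs and SAEs, but no any-local, any-general or any-symptom composite. The individual solicited symptoms already use completed screens.

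Inversion of a composite and its component is possible, but it needs a symptom close to the composite as well as enough missing screens.

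**Conclusion.** The point holds in conditional form and is minor. If any vaccinated subjects have neither a symptom screen nor another recorded Day 1-4 event of the kind summarised, the combined percentages in section 10.8 are understated by s × m. If s is assumed to be 70%, that is 0.7 to 1.4 points at m = 1-2% and 3.5 points at m = 5%. For low-rate versions it is negligible, and at m = 0 there is no error. The values of r, s and m are assumptions, since the protocol gives none of them.

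The study has a single arm, section 10.9 makes all analysis descriptive, and no test or comparison uses these figures. No primary or listed secondary result changes.

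**What to change.** In section 10.5, state that the combined Day 1-4 summaries, including the grade 3, related and medical-consultation versions, are tabulated on subjects with a completed symptom screen alongside the all-vaccinated percentage. Give the number of vaccinated subjects without a completed screen. Leave unsolicited AEs and SAEs on all vaccinated subjects.

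The cost is one wording change, one denominator flag and one extra column, with no new data. The downside is that the completed-screen rate is unbiased only if non-return is unrelated to symptoms. Keeping the all-vaccinated column also keeps events recorded in subjects without a screen in the tabulated rates, and the count of missing screens lets a reader judge how far the two percentages could mislead.

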10.6. Analysis of demographics

Demographic characteristics (age at vaccination visit in years, gender and geographical ancestry, body mass index in kg/m²), cohort description and withdrawal status will be summarised using descriptive statistics:

- Frequency tables will be generated for categorical variable such as centre.
- Mean, median, standard deviation will be provided for continuous data such as age.
- The distribution of subjects based on age stratification will be tabulated (as seen in [Table 23](#)).

In addition, the above analysis will also be done for sub-groups based on age as an exploratory analysis.

Table 23 Age stratification

Age groups	Number of subjects
4-9 years	~112
10-17 years	~112
18-64 years	~112
≥65 years	~112

10.7. Analysis of immunogenicity

The primary analysis will be based on the PP cohort for analysis of immunogenicity. If, the percentage of vaccinated subjects with serological results excluded from the PP cohort for analysis of immunogenicity is 5% or more, a second analysis based on the TVC will be performed to complement the PP analysis.

For all subjects and each antigen:

- Seropositivity/seroprotection rate at pre-vaccination and one month post-vaccination will be calculated with exact 95% CIs.
- GMCs at pre-vaccination and one month post-vaccination will be tabulated with 95% CIs.
- Booster response rate one month post-vaccination will be calculated with exact 95% CIs for diphtheria, tetanus and pertussis antigens.

In addition, the above analysis will also be done based on age stratification (Refer [Table 23](#)) as an exploratory analysis.

Finally, antibody concentrations distribution at pre-vaccination and one month post-vaccination will be displayed using reverse cumulative curves (RCC).

10.8. Analysis of safety

The analysis will be based on the TVC.

- The percentage of subjects reporting each individual solicited local and general symptom during the 4-day (Day 1-4) follow-up period after booster vaccination will be tabulated. The same calculations will be done for each individual solicited symptom rated as grade 3 in intensity and for each individual solicited symptom assessed as causally related to vaccination.
- Occurrence of fever during the 4-day follow-up period after vaccination will be reported per 0.5°C cumulative increments.
 - In addition, the above analysis will also be done for sub groups based on age stratification (Refer [Table 23](#)) as an exploratory analysis.
- The percentage of subjects with at least one local symptom (solicited or unsolicited), with at least one general symptom (solicited or unsolicited) and with any symptom (solicited or unsolicited) during the 4-day (Day 1-4) follow-up period after booster vaccination will be tabulated with exact 95% CI after booster vaccination. The same calculations will be done for symptoms (solicited or unsolicited) rated as grade 3 in intensity, for symptoms (solicited or unsolicited) leading to medical consultation and for symptoms (solicited or unsolicited) assessed as causally related to vaccination.
- The percentage of subjects who started to receive at least one concomitant medication (i.e. any medication, antipyretic medication, prophylactic antipyretics) during the 4-day (Day 1-4) and 31-day (Day 1-31) follow-up period after vaccination will be tabulated with exact 95% CI.

- The verbatim reports of unsolicited AEs will be reviewed by a clinical research and development lead and the signs and symptoms will be coded according to MedDRA. Every verbatim term will be matched with the appropriate Preferred Term. The percentage of subjects with unsolicited AEs occurring within the 31-day (Day 1-31) follow-up period after booster dose with its exact 95% CI will be tabulated by Preferred Term. Similar tabulation will be done for unsolicited AEs rated as grade 3 and for unsolicited AEs with causal relationship to vaccination.
- Any large injection site reaction (for subjects <6 years of age defined as a swelling with a diameter of >50 mm and for subjects ≥6 years of age swelling with a diameter of >100 mm, noticeable diffuse swelling or noticeable increase in limb circumference) onset during the 4-day (Day 1-4) follow-up period after vaccination will be described in detail.
- SAEs and withdrawal due to AEs and SAEs will be described in detail.

10.9. Interpretation of analyses

All analysis will be conducted in a descriptive manner.

10.10. Conduct of analyses

Any deviation(s) or change(s) from the original statistical plan outlined in this protocol will be described and justified in the final study report.

10.10.1. Sequence of analyses

Analysis of the single booster dose will be performed at the end of the study when all data are available. An integrated clinical study report containing all data will be written and made available to the investigators.

10.10.2. Statistical considerations for interim analyses

All analyses will be conducted on final data and therefore no statistical adjustment for interim analyses is required.

11. ADMINISTRATIVE MATTERS

To comply with ICH GCP administrative obligations relating to data collection, monitoring, archiving data, audits, confidentiality, public disclosure requirements and publications must be fulfilled.

11.1. Electronic Case Report Form instructions

A validated GSK defined electronic data collection tool will be used as the method for data collection.

In all cases, subject initials will not be collected nor transmitted to GSK. Subject data necessary for analysis and reporting will be entered/transmitted into a validated database or data system. Clinical data management will be performed in accordance with applicable GSK standards and data cleaning procedures.

While completed eCRFs are reviewed by a GSK Biologicals' Site Monitor at the study site, omissions or inconsistencies detected by subsequent eCRF review may necessitate clarification or correction by the investigator or appropriately qualified designee. In all cases, the investigator remains accountable for the study data.

The investigator will be provided with a CD-ROM of the final version of the data generated at the investigational site once the database is archived and the study report is complete and approved by all parties.

11.2. Study Monitoring by GSK Biologicals

GSK will monitor the study to verify that, amongst other items, the:

- Data are authentic, accurate, and complete.
- Safety and rights of subjects are being protected.
- Study is conducted in accordance with the currently approved protocol, any other study agreements, GCP and all applicable regulatory requirements.

The investigator and the head of the medical institution (where applicable) agrees to allow the monitor direct access to all relevant documents.

The investigator must ensure provision of reasonable time, space and qualified personnel for monitoring visits.

Direct access to all study-site related and source data is mandatory for the purpose of monitoring review. The monitor will perform eCRF review and a Source Document Verification (SDV). By SDV we understand verifying eCRF entries by comparing them with the source data that will be made available by the investigator for this purpose.

The Source Documentation Agreement Form describes the source data for the different data in the eCRF. This document should be completed and signed by the site monitor and investigator and should be filed in the investigator's study file. Any data item for which the eCRF will serve as the source must be identified, agreed and documented in the source documentation agreement form.

Upon completion or premature discontinuation of the study, the monitor will conduct site closure activities with the investigator or site staff, as appropriate, in accordance with applicable regulations, GCP, and GSK procedures.

11.3. Record retention

Following closure of the study, the investigator must maintain all site study records (except for those required by local regulations to be maintained elsewhere) in a safe and secure location. The records must be easily accessible, when needed (e.g. audit or inspection), and must be available for review in conjunction with assessment of the facility, supporting systems, and staff. Where permitted by applicable laws/regulations or institutional policy, some or all of these records can be maintained in a validated format other than hard copy (e.g. microfiche, scanned, electronic); however, caution needs to be exercised before such action is taken. The investigator must ensure that all reproductions are legible and are a true and accurate copy of the original and meet accessibility and retrieval standards, including re-generating a hard copy, if required. Furthermore, the investigator must ensure that an acceptable back-up of the reproductions exists and that there is an acceptable quality control procedure in place for making these reproductions.

GSK will inform the investigator/institution of the time period for retaining these records to comply with all applicable regulatory requirements. The minimum retention time will meet the strictest standard applicable to a particular site, as dictated by ICH GCP, any institutional requirements, applicable laws or regulations, or GSK standards/procedures, otherwise, the minimum retention period will default to 25 years after completion of the study report.

The investigator/institution must notify GSK of any changes in the archival arrangements, including, but not limited to archival at an off-site facility, transfer of ownership of the records in the event the investigator leaves the site.

11.4. Quality assurance

To ensure compliance with GCP and all applicable regulatory requirements, GSK may conduct a quality assurance audit. Regulatory agencies may also conduct a regulatory inspection of this study. Such audits/inspections can occur at any time during or after completion of the study. If an audit or inspection occurs, the investigator and institution agree to allow the auditor/inspector direct access to all relevant documents and to allocate his/her time and the time of his/her staff to the auditor/inspector to discuss findings and any relevant issues.

11.5. Posting of information on publicly available clinical trial registers and publication policy

GSK assures that the key design elements of this protocol will be posted on the GSK website and in publicly accessible database(s) such as clinicaltrials.gov, in compliance with the current regulations.

GSK also assures that results of this study will be posted on the GSK website and in publicly accessible regulatory registry(ies) within the required time-frame, in compliance with the current regulations. The minimal requirement is to have primary endpoint summary results disclosed at latest 12 months post PCD and to have secondary endpoint

disclosed at latest 12 months after the last subject last visit (LSLV) as described in the protocol.

GSK also aims to publish the results of these studies in searchable, peer reviewed scientific literature and follows the guidance from the International Committee of Medical Journal Editors.

11.6. Provision of study results to investigators

Where required by applicable regulatory requirements, an investigator signatory will be identified for the approval of the study report. The investigator will be provided reasonable access to statistical tables, figures, and relevant reports and will have the opportunity to review the complete study results at a GSK site or other mutually-agreeable location.

GSK Biologicals will also provide the investigator with the full summary of the study results. The investigator is encouraged to share the summary results with the study subjects, as appropriate.

